Appendix

Pharmacy Instructions for NICHD Protocol

Aim 2: Prevention of Neonatal Abstinence Syndrome (NAS2)

Double-blind study therefore only the pharmacist will know which study medication (ondansetron or placebo) the pregnant woman will receive; the neonate is assigned the same study medication their mother received. (Only one randomization number for the maternal/neonate pair).

Pregnant women randomized to IV ondansetron:

- The IV dose of ondansetron will always be 8mg per dose (ondansetron concentration is 2mg/mL, thus 4 mL = 8mg)
- The **woman's dose may be repeated one time** if she does not deliver her baby within 4 hours of the first dose of ondansetron.

Pregnant women randomized to IV placebo:

- **IV placebo** is prepared to "mimic the volume" of the 8mg dose of ondansetron.
- Prepare **IV placebo** with **normal saline 4 mL** (0.9% Sodium Chloride injection).
- The **pregnant woman's dose may be repeated one time** if she does not deliver her baby within 4 hours of the first dose of placebo.

Neonates assigned to ondansetron:

- Dose is based on **birth weight**.
- **Oral dose is 0.07 mg/kg every 24 hours** starting the day of birth, between 4-8 hours of life, and continuing for a maximum of 5 doses of study medication.
- Concentration of oral ondansetron 0.8 mg/mL
- **IV dose is 0.04 mg/kg every 24 hours** starting the day of birth, between 4-8 hours of life, and continuing for a maximum of 5 doses of study medication.
- The route of dosing may start with oral or IV doses or may be switched from oral to IV dosing at any time if the NICU/Research teams believe it is best for the baby.
- Concentration of IV ondansetron is 2mg/mL

Neonates assigned to placebo:

- Dose is based on the **birth weight**.
- **Simple Syrup** will be used for **oral placebo** doses. (Manufacturer: Humco. NDC # 0395-2661-16; 16 oz bottle)
- **Oral placebo** must "mimic the volume" of a dose of ondansetron, as if the baby had been assigned to oral ondansetron 0.07 mg/kg.
- **Normal saline** (0.9% Sodium Chloride injection) will be used for **IV placebo** doses.
- **IV Placebo** must "mimic the volume" of a dose of ondansetron, as if the baby had been assigned to IV ondansetron 0.04 mg/kg per dose.

AIM 2- Prevention of Neonatal Abstinence Syndrome

Statistical Analysis Plan

NCT01965704

March 30, 2022

Only infants who received at least one dose of study medication and met the inclusion criteria were included in the efficacy analysis. All infants and mothers who were allocated and received at least one dose of study medication were included in the safety analysis. Power analysis effect size was based upon NPOW response data that was obtained from the healthy opioid-naïve adult volunteers under controlled conditions. In that study, there was a difference of 2.38 between the means of the control and ondansetron-treated withdrawal responses, with standard deviations of 2.23 and 0.89, respectively. Based upon these numbers, 13 patients per treatment arm would have 90% power to ensure that a treatment difference (ondansetron vs. control) could be detected at the $p=0.05$ level. However, because of the very large of differences between opioid-naïve adults analyzed under experimentally controlled conditions and infants that are exposed *in utero* to opioids, the actual relative effect size of ondansetron treatment was assumed to be 25-33% of that estimated from the pilot data in normal subjects. This revised effect size estimate provided 45 infants in each arm to provide the same statistical power. For the categorical outcomes in the primary and secondary endpoints (the fraction of infants requiring pharmacologic therapy with morphine and the need for adjunctive phenobarbital or clonidine therapy), Fisher's Exact test was used to perform the analysis of independence. Because the need for morphine was not impacted by the sex of the neonates or by the race/ethnicity of the mother, these stratification factors were not corrected for in the analysis of primary outcome.

The null hypothesis for the Fisher's Exact test was that the need for morphine treatment and study drug allocation were independent. The continuous outcomes of secondary endpoints were examined using the two-sided Wilcoxon Rank-Sum test (equivalent to the Mann-Whitney test), where the null hypothesis is stated as the outcomes in the ondansetron and placebo arms are equal. Inclusion of neonates in the safety population was based upon receipt of ondansetron in any form (study drug administered to infant or exposure through maternal transfer). QTc values in the safety population were analyzed by two sample t-test to determine if the mean QTc of two groups were equal. All tests were two-sided, and the p-values obtained from statistical tests were compared with the significance level ($\alpha =0.05$) to determine whether null hypothesis could be rejected or retained. Statistical analyses were performed using R software (version 3.6.1).

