- a. ECG: The neonate will be stabilized after birth and then will receive a screening 12-lead ECG to rule out QTc Bazett greater than or equal to 480ms. Once the neonate is medically stable and a normal QTc confirmed by the treating physician, the neonate will receive the same 'blinded' study drug (ondansetron or placebo) as his or her mother; this first dose of study drug is to be given between 4-8 hours after delivery. A repeat 12-lead ECG will be done on all neonates following each of the 5 doses of study drug, between 2-5 hours after each dose of study drug. Any neonate that shows significant ECG changes will be excluded from further dosing of study medication but will continue safety follow-up.
 - i. If the QTc is prolonged, the neonate will be transferred to the NICU for continuous cardiac monitoring, if the standard of care indicates the neonate should be admitted to NICU; this will be determined on a case-by-case basis at each site. In addition, a blood test to check the potassium, magnesium, calcium, and ionized calcium levels will be done if the clinical team believe it is necessary for the neonates safety; if the levels are abnormal, electrolytes will be normalized using IV or oral supplements as indicated per standard of care.
 - ii. All ECGs, from all sites, will be sent to Stanford to be interpreted by a cardiologist, who is not a member of the study team, to confirm the accuracy, and consistency of the initial readings.
- b. Standard of Care for Well Baby Nursery:
 - i. Vital Signs: heart rate (HR), respiratory rate (RR), and temperature will be monitored every 4-8 hours depending on the infant's history, and blood pressure at least once per day.
 1. If the HR is less than 80 beats per minute, a rhythm strip or 12-lead ECG is ordered to evaluate the QTc interval, a Neonatal Intensive Care Unit (NICU) physician will assess the neonate and a blood pressure will be obtained.
 2. If the QTc is prolonged, see "ECG" above which discusses the possibility of the neonate being transferred to the NICU for continuous cardiac monitoring if deemed necessary by standard of care
 - ii. A member of the study team will visit the Well Baby Nursery at least once per day to ensure the neonate is doing well and that everyone on the clinical team understands the protocol and knows how to contact the principal investigator to answer questions as needed.

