Interim Analysis: an interim analysis will be performed after a total of twenty (20) pregnant women and their twenty (20) neonates have been enrolled and dosed with study medication. The analysis will include all the ECG measurements, blood concentration levels for pharmacokinetics (PK) and a reassessment of the PK of ondansetron in neonates, all to be reviewed by the DSMB. The study will only proceed if the DSMB gives their approval. These 20 neonates will be the “First cohort” of neonatal patients. (Note, this was done between April and May 2016)

B. Study Medication Dosing

Adult Pregnant Participant’s Dose: The amount and timing of the dose of ondansetron to be administered to the pregnant participants, who are randomized to the ondansetron group, will be 8 mg (IV) within 4 hours of delivery. Should the participant be undelivered 4 hours following the initial dose of study drug, a second dose will be administered. The study medication will be delivered intravenously to the mother prior to either vaginal or cesarean delivery. Exception: if the pregnant participant does not want to receive any study medication prior to delivery because she is not experiencing nausea, she may still continue to be a part of the study and her neonate will be assigned to the study medication she would have been randomized to receive. This allows for an adult patient to not be given the study medication

(ondansetron or placebo) if they feel they do not need it. The neonate's participation will continue as planned.

Neonatal Participant's Dose: The neonates who are born to the mothers, who are randomized to receive ondansetron, will have an initial oral dose of ondansetron 0.07 mg/kg given between 4-8 hours after delivery. The subsequent doses of ondansetron will be 0.07 mg/kg orally every 24 hours for up to 5 doses maximum.

The timing and volume of placebo administration for the 50% of subjects in the placebo group will mimic that of the 50% of subjects in the ondansetron group. Placebo will consist of either normal saline for IV administration or inactive oral syrup for oral administration.

For those neonates who require an intravenous catheter for any other medical reason, these neonates will receive an ondansetron dose of 0.04 mg/kg IV every 24 hours for up to 5 doses maximum.

C. Study Procedures

Adult Pregnant Participant's Procedures:

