2.1.2 Inclusion/Exclusion

Criteria

Subjects	Inclusion Criteria	Exclusion Criteria
Maternal/Paternal	Women of reproductive age (18-45 years old, inclusive) and their fetuses/neonates. Daily opioid use for at least 3 weeks prior to delivery Gestational age of \geq 37 weeks to < 42 weeks at delivery. Competent mother willing to sign the informed consent for herself and both parents competent and willing to sign consent/permission for their neonate.	Any condition that, in the opinion of the investigator, would compromise the health of the participant (both mother and fetus) or the integrity of the data. Known allergy to the study medication. Screening 12-lead ECG, if done, showing prolonged QTc will stop the mother from receiving any study drug but her neonate can still be included in the study. Maternal ingestion or administration of ondansetron within 24 hours prior to delivery, for reasons other than study purposes, will exclude the mother and neonate.
Neonatal	Participating mother Maternal (and paternal if	QTcB greater than or equal to 480ms on any 12-lead

	present and competent) consent	ECG post delivery will stop the dosing of the study drug, but safety follow up will be done including blood samples & 12-lead ECG(s) if the mother or baby received at least one dose of study drug.
--	-----------------------------------	---

This study will include special classes of participants: pregnant women and their newborns. The focus of this study is specific to these sensitive populations of pregnant women and neonates and as such warrants their inclusion. We feel that, in balance, the potential for significant benefit to the neonatal population in this study and in future patients outweighs the risks (section 5.0 *Potential Risks* below).

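### The efficacy set drops randomised infants who fail the post-birth QTc screen and are never dosed, even when the mother received allocated drug, and no as-randomised analysis is planned

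*SAP*

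**What the plan says.** The SAP's opening paragraph defines the efficacy population: "Only infants who received at least one dose of study medication and met the inclusion criteria were included in the efficacy analysis". For safety, the SAP's second paragraph counts a neonate as exposed on a wider basis: "study drug administered to infant or exposure through maternal transfer". The primary null hypothesis is that "the need for morphine treatment and study drug allocation were independent".

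The protocol sets the order of events. Section 2.1.1 randomises the mother-infant pair after admission to labor and delivery, and the pharmacy appendix gives the pair one randomisation number. Section 2.1.1 B says of maternal dosing: "The study medication will be delivered intravenously to the mother prior to either vaginal or cesarean delivery". After birth, under section 2.1.1 A, the neonate "will receive a screening 12-lead ECG to rule out QTc Bazett greater than or equal to 480ms". Section 5.0 requires this ECG to be read before any neonatal study drug is given. The neonatal entry in the exclusion column of section 2.1.2 says that a QTcB at or above the limit on any "ECG post delivery will stop the dosing of the study drug". Safety follow-up then continues if either the mother or the baby had been dosed.

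**The concern.** Section 1.0 describes the tested regimen as a maternal dose just before delivery followed by several days of neonatal dosing. Treatment therefore starts with the mother. The infant's QTc is measured after that exposure has begun, and the result decides whether the infant gets a first dose. The SAP then requires that dose for entry to the efficacy set.

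Where the mother was dosed, membership of the primary comparison thus depends on a measurement that the allocated drug could affect. The plan treats a drug effect on QTc as an open question, since it tests the safety population "to determine if the mean QTc of two groups were equal". Blinding stops staff from choosing whom to exclude, but it does not stop the drug from changing who is excluded. If the infants screened out differ between arms in number or in underlying need for morphine, the comparison is no longer the randomised one. With about 45 infants per arm, a few such infants could alter a borderline result. The reader would have neither counts of undosed infants by arm nor an as-randomised result with which to judge.

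**Working it through.** **Structure**

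1. Randomisation: one allocation per pair, before birth (protocol 2.1.1; pharmacy appendix).
2. Maternal study drug: before delivery (2.1.1 B).
3. Neonatal ECG: after birth, read before the first neonatal dose (2.1.1 A; 5.0).
4. QTcB of 480 ms or more at that ECG: no neonatal dose, safety follow-up only (2.1.2).
5. Efficacy set: requires at least one infant dose (SAP). The infant in step 4 is out.

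Section 2.1.2 itself foresees a dosed mother with an undosed baby, because it ties safety follow-up to a dose in either of them. The pathway has limits. It does not arise when the mother received no study drug. It does not remove an infant whose QTcB first reaches 480 ms after a dose, because that infant has already qualified.

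**Bias within one arm**

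Let e be the share of the arm undosed, p the morphine rate in all randomised infants of the arm, q the rate in undosed infants, and r the rate in those included. Then p = (1 − e)r + eq, so

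r − p = e(p − q)/(1 − e).

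This is zero when q = p. Suppose there is no true effect, infants are dropped from one arm only, and their risk differs from the arm average by 20 to 30 points (assumed). The risk difference then shifts as follows:

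- 5% dropped: 0.05 × 0.20/0.95 = 1.1 points, to 0.05 × 0.30/0.95 = 1.6 points
- 10% dropped: 2.2 to 3.3 points
- 20% dropped: 5.0 to 7.5 points

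**Effect on the planned test**

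The inputs from the SAP are 45 infants per arm, the two-sided Fisher exact test and alpha 0.05. Assumed inputs are placebo morphine rates of 60%, 69% and 80%, and a just-significant result in the analysed set. These rates lie inside the 42–94% range that section 1.0 gives for NAS. The k undosed ondansetron infants, all assumed to need morphine, are then added back.

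| Analysed set (ondansetron vs placebo) | Fisher p | k (share of arm) | One arm restored | Fisher p | Risk difference, points |
|---|---|---|---|---|---|
| 16/45 vs 27/45 | 0.034 | 2 (4.3%) | 18/47 vs 27/45 | 0.060 | −24.4 → −21.7 |
| 20/45 vs 31/45 | 0.033 | 3 (6.3%) | 23/48 vs 31/45 | 0.058 | −24.4 → −21.0 |
| 26/45 vs 36/45 | 0.040 | 4 (8.2%) | 30/49 vs 36/45 | 0.070 | −22.2 → −18.8 |

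The bias formula agrees. In the first row e = 2/47, p = 18/47 and q = 1, so r − p = (2/47)(18/47 − 1)/(45/47) = −2.7 points.

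**Sensitivity of these tables**

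- One infant fewer added back: p = 0.036, 0.037, 0.045, all still significant.
- Same k added to both arms, all needing morphine: 18/47 vs 29/47, p = 0.039; 23/48 vs 34/48, p = 0.037; 30/49 vs 40/49, p = 0.043.
- Uncorrected chi-square in the one-arm tables: 0.020 → 0.037, 0.019 → 0.041, 0.023 → 0.047. It passes 0.05 only at k = 4, 4 and 5, so part of the Fisher crossing is discreteness.

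**The case against.** The strongest reply is that a dosed-infant set is a recognised modified intention-to-treat choice in a blinded trial. QTcB of 480 ms or more is listed in the exclusion column, and maternal dosing is optional. On this view the infant is the real participant, and nothing in the documents shows that screen failures differ by arm or relate to morphine need. The SAP never names the QTc screen as a reason for leaving the efficacy set. Its QTc t-test is an ordinary safety comparison, not evidence that maternal drug causes failed screens. The reference to allocation in the null hypothesis names the comparison, not the population, and the protocol's endpoint wording about enrolled neonates does not define an analysis set.

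The worst case is also fragile. It starts from barely significant tables, puts every undosed infant in one arm and gives all of them morphine. If one restored infant did not need morphine, all three tables stay significant (p = 0.036, 0.036, 0.044).

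Much of this stands as a limit on size. It does not remove the structural point. The modified set is safe only if non-dosing is unaffected by allocation, and here the deciding measurement follows the maternal dose. Placing the rule in the exclusion column does not make it a baseline fact, since it is worded as stopping dosing. One could read receipt of a dose as including transfer from the mother. That reading is strained, because the SAP spells out maternal transfer only for safety; if it was meant, the SAP needs to say so.

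The part of the protocol between sections 2.1.2 and 4.0 was not available, so the absence of an as-randomised analysis is established only for the text supplied.

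**Conclusion.** The concern holds. On the natural reading of the SAP, the primary analysis excludes randomised infants on a post-randomisation event that the allocated treatment may affect, and the supplied text contains no as-randomised check.

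The actual size and direction cannot be determined. Apart from dilution, there is no bias if the exclusions are balanced by arm with equal risk, or if they are unrelated to morphine need. The shift of 2.7 to 3.5 points and the loss of Fisher significance are a one-arm worst case resting on the assumed rates and counts, not an estimate. The point should be addressed, but it does not by itself invalidate the trial. Confidence is medium because the frequency of undosed infants is unknown.

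**What to change.** Add an analysis of the primary endpoint in all randomised pairs with a live-born infant, by assigned arm, whether or not the infant was dosed. Leave out only pairs ineligible on facts fixed before randomisation.

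Make this the primary analysis only if outcomes have not been unblinded. Otherwise keep the current set as primary, report the new analysis beside it, and state when it was added. The second route may be the one that applies: the SAP is written in the past tense and already reports a finding on morphine need ("Because the need for morphine was not impacted by the sex of the neonates").

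Either way, tabulate undosed infants by arm and reason, state how many had a mother who received study drug, and bound the result where an outcome cannot be retrieved.

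The cost is one analysis, one table and limited record retrieval. NAS treatment data are already planned items (protocol 2.1.1 A and 4.3), but section 2.1.2 promises only safety follow-up after a QTcB failure, so a few outcomes may have to be fetched. The downside is some dilution of the effect from undosed infants. Further dilution could come from pairs in which the mother took non-study ondansetron after randomisation, whom section 2.1.2 excludes but an as-randomised analysis would keep. An analysis added after unblinding is supportive only. No change to dosing or to the ECG rule is involved.

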1.0 Background and Purpose

The misuse of and addiction to opioid medications has become the most rapidly increasing drug problem in the US, which has consequences for pregnant mothers and their babies. The prevalence of maternal opioid drug use at the time of delivery in California is approximately one percent. The neonatal abstinence syndrome (**NAS**) is a constellation of narcotic drug withdrawal symptoms that develops in 42 to 94 percent of infants born to narcotic dependent mothers. There are no preventative treatments for this severe syndrome, which can result in a prolonged hospitalization and treatment in a neonatal intensive care unit.

Based upon a genetic discovery, we demonstrated that administration of a 5-HT3 antagonist (ondansetron) prevented the symptoms of narcotic drug withdrawal in experimental studies in mice and in humans. From this, we hypothesize that ondansetron administration to pregnant narcotic-using mothers just prior to delivery, followed by a 3 to 5-day period of ondansetron

administration to the neonate, could reduce the incidence or severity of NAS symptoms. Ondansetron is a broadly utilized drug with a substantial safety record in pregnant women. We now understand the pharmacokinetics of ondansetron at birth based on PK analysis of placental and neonatal blood samples in babies whose mothers' were given ondansetron prophylactically prior to cesarean delivery (Aim 1 of the protocol, Prevention of Neonatal Abstinence Syndrome). In this study, (Aim 2) we will conduct a multi-center, randomized, double blind, and placebo-controlled trial to determine whether ondansetron treatment will reduce the incidence (percentage of infants requiring narcotic drug treatment) or severity (total amount of narcotic drug required, length of hospitalization, symptom severity scores) of NAS in babies born to narcotic-using mothers.

This project tests a very novel approach for preventing an important pregnancy-related complication of narcotic drug abuse. If a brief period of ondansetron administration to the mothers that use narcotic drugs, and to their babies, can prevent or ameliorate the development of narcotic drug withdrawal symptoms in neonates, this would reduce human suffering and the growing societal cost of opiate abuse.

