6. Follow-up calls/visits: a research team member will call the mother of the baby once they have been discharged home, if the baby is discharged prior to Day 15 of their life. We want to follow up on the babies and learn how they are doing and make sure they are not going into "Delayed" NAS. For babies who are discharged early it is more likely they could go into delayed NAS and that is why we plan to call the mothers daily, for up to 10 days after the baby takes their last dose of study medication, to ask about their baby's status. We are interested in how the baby is feeding, are they breast or bottle feeding the baby, what is the baby's mood (crying excessively, fussy, agitated), sleeps for how many hours after feeding, sneezing a lot, sweating, vomiting, gaining weight, loose stools or watery stools, etc. We also need to ask the mother all the medications she is taking, if she is breastfeeding her baby, since we know these medications will enter the baby's system through the breast milk. If a baby is not discharged before day 15 of their life, the research team member will visit the baby in the hospital daily, for 10 days after their last dose of study drug, to check on the status of the baby from the clinical team caring for the baby. If the mother is home while the baby remains hospitalized, the research team member will also call the mother on a daily basis to maintain contact and to ask the mother all the medications she is taking if she is breastfeeding her baby (we know these medications may enter the baby's system through the breast milk).

7. The final follow-up call (or visit if the baby is still in the hospital) will occur approximately 30 days after the baby's last dose of study medication; this call (or visit) will be to determine if any previously reported adverse events have resolved and/or if any new adverse events have occurred since the last follow-up call or visit.

The primary endpoint will be the incidence of NAS in enrolled neonates and will be measured by the need for pharmacologic treatment for the symptoms of NAS (Morphine). The secondary endpoint of the severity of NAS will be measured by the length of the hospitalization (birth to discharge), the total dose of narcotic required to treat the symptoms of NAS, and the need to include barbiturates in the treatment of symptoms of NAS.

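### The SAP's 90% power is for a mean withdrawal score in adult volunteers; it does not describe the primary comparison, Fisher's exact test on need for morphine

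*SAP*

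**What the plan says.** **Power basis.** The SAP states: "Power analysis effect size was based upon NPOW response data that was obtained from the healthy" volunteers, who had no opioid dependence. The pilot result is given as follows: "there was a difference of 2.38 between the means of the control and ondansetron-treated withdrawal responses". The two SDs were 2.23 (control) and 0.89 (ondansetron), and on this basis "13 patients per treatment arm would have 90% power" at the 0.05 level. The SAP then takes the effect in exposed infants to be 25 to 33% of the pilot effect and concludes: "This revised effect size estimate provided 45 infants in each arm to provide the same statistical power". It does not say which endpoint the 45 per arm refers to.

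**Primary endpoint.** Protocol section 2.1.1, at the end of the study procedures, says: "The primary endpoint will be the incidence of NAS in enrolled neonates and will be measured by the need for pharmacologic treatment", and names morphine.

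**Primary test.** For this outcome and the other categorical ones, the SAP says that Fisher's "Exact test was used to perform the analysis of independence". All tests are two-sided at 0.05.

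**Data collected.** Protocol sections 2.1.1 and 4.3 list Modified Finnegan scores for the neonates. NPOW is not listed for mothers or infants.

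**Nearest figure to a control rate.** Protocol section 1.0 says that NAS "develops in 42 to 94 percent of infants born to narcotic dependent mothers". That is how often the syndrome occurs, not how often morphine is needed.

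**The concern.** A power statement belongs to one outcome, one test and one assumed effect. Here the outcome is a continuous score in adults and the comparison is of two means, while the trial's decision rests on two proportions compared by Fisher's exact test. Power for that test needs a control proportion and a target difference, and the SAP's power paragraph gives neither.

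What is at stake is how a non-significant result is read. The SAP compares p-values with 0.05 to reject or retain the null, and the available text plans no confidence interval for the primary effect. A reader told that the trial has 90% power could take a retained null as evidence that ondansetron does little, although a sizeable fall in morphine need might well have been missed.

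**Working it through.** **1. Reproduce the SAP's own figures.** Inputs from the SAP: difference 2.38, SDs 2.23 and 0.89, two-sided 0.05, 90% power.

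- Pooled SD = sqrt((2.23² + 0.89²)/2) = 1.698, so d = 2.38/1.698 = 1.402.
- Normal formula: n = 2(1.960 + 1.282)²/d² = 21.01/1.965 = 10.7, so 11 per arm. The equal-variance t test gives 12. The Welch t test gives 13, with 91.8% power at 13. The pilot figure of 13 reproduces.
- 25 to 33% of the pilot effect is d = 0.350 to 0.463. The same formula gives 21.01/0.350² ≈ 171.1, so 172 per arm, and 21.01/0.463² ≈ 98.2, so 99 per arm (173 and 100 with the t test). The figure of 45 does not reproduce; at 45 per arm the power for the continuous score is about 37 to 59%. This scaling error is a separate matter, but it has to be kept apart from the present point (step 4).

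**2. What 45 per arm can detect on the primary test.** Two-sided Fisher power was enumerated exactly over all 46 × 46 outcome tables. The only outside assumption is the control rate, run over 42 to 94%.

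| Control rate | Treated rate for 90% power (drop) | Treated rate for 80% power (drop) |
|---|---|---|
| 42% | 10.9% (31.1 points) | 14.0% (28.0) |
| 60% | 24.7% (35.3) | 28.7% (31.3) |
| 70% | 34.1% (35.9) | 38.5% (31.5) |
| 80% | 46.0% (34.0) | 50.6% (29.4) |
| 94% | 66.2% (27.8) | 70.4% (23.6) |

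Check: 70% to 34% gives 90.2% power, and 70% to 38.5% gives 80.0%.

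**3. Illustration only: carrying the reduced effect to a yes/no outcome.** This needs a conversion that the SAP does not supply. Two were tried: a latent-normal shift, p_t = Φ(Φ⁻¹(p_c) − d), and a logistic shift, log odds ratio = −dπ/√3. Fisher power at 45 per arm:

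| Control rate | Latent-normal, d = 0.350 | Latent-normal, d = 0.463 | Logistic, d = 0.350 | Logistic, d = 0.463 |
|---|---|---|---|---|
| 42% | 19% | 32% | 23% | 38% |
| 60% | 19% | 32% | 24% | 40% |
| 70% | 19% | 33% | 24% | 40% |
| 80% | 16% | 28% | 18% | 33% |
| 94% | 7% | 13% | 5.5% | 11% |

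The ranges are about 7 to 33% and about 5 to 41% (the last value at exactly one third of the pilot effect). The latent-normal drops are 5 to 18 points. At 60 per arm, the protocol's ceiling of 120 pairs, the ranges are about 10 to 47% and 8 to 58%.

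**4. Separate the endpoint mismatch from the scaling error.** Take the sizes that do give 90% power on the continuous score (173 per arm at d = 0.350, 100 at d = 0.463) and apply the latent-normal conversion. Fisher power is then:

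| Control rate | 173 per arm, d = 0.350 | 100 per arm, d = 0.463 |
|---|---|---|
| 42% | 68% | 65% |
| 60% | 69% | 71% |
| 70% | 68% | 68% |
| 80% | 62% | 62% |
| 94% | 36% | 37% |

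The mismatch alone therefore lowers 90% to about 62 to 71% for control rates of 42 to 80%, and to 36 to 37% at 94%. The rest of the shortfall in step 3 comes from the scaling error.

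**The case against.** The strongest case on the other side has five parts.

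- **The tempting headline is not a document figure.** A reader might infer that the primary test has only 7 to 33% power under the SAP's own assumed effect. The SAP assumes a fraction of an NPOW effect. It never treats morphine need as a threshold on a latent severity scale, and the protocol ties morphine to each hospital's guidelines, Finnegan score and clinical assessment. The figure depends on the conversion chosen and on a borrowed NAS incidence, and it mixes in the scaling error. This objection stands, so steps 3 and 4 are illustrative only.
- **Absence.** Protocol section 3.0 was not in the available text, so it cannot be said that the full protocol lacks a control rate or target difference. This also stands. The SAP's power paragraph, however, is available and gives neither.
- **A different reading of the discount.** If the pilot effect were reduced by 25 to 33%, so that 67 to 75% is kept, latent-normal Fisher power at 45 per arm would be about 71 to 96%. The SAP's words say that 25 to 33% of the effect remains, so this reading fails.
- **Disclosure and timing.** The SAP openly names its NPOW source, and misreading of a null result is a prediction. The SAP is dated March 30, 2022 and written in the past tense, so enrolment can no longer change, and a control rate picked now could be guided by the data. These points limit the remedy to wording and reporting.
- **Validity.** Neither Fisher's test nor its type I error is affected. That is correct, and nothing here says otherwise.

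**Conclusion.** The point holds. The 90% is the power of a comparison of mean NPOW scores and cannot be read as power for need for morphine. This conclusion comes from the documents' wording and needs no conversion.

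Its size is best given by the detectable differences in step 2, which rest only on 45 per arm, two-sided 0.05 and control rates assumed to span 42 to 94%. The documents do not support a single power value for the primary test. They support only the statement that the available text gives none, and that the illustrative values tried at the stated 25 to 33% fall well short of 90%, partly for a separate reason.

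**What to change.** Revise the SAP's power paragraph and the primary reporting as follows.

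1. Stop presenting 90% as the trial's power. Keep the NPOW calculation, labelled as the historical rationale for the number enrolled.
2. State what the primary test can detect over a range of control rates, labelled as assumed and not chosen from the observed data. Possible wording: *With 45 infants per arm, a two-sided Fisher's exact test at 0.05 has 90% power for a fall in morphine need from an assumed 70% to 34%, and 80% power for a fall from 70% to 38.5%.* Give the same figures for other rates between 42% and 94%. The 70% is an example and is not taken from the documents.
3. Report the risk difference in morphine need with its 95% CI beside the Fisher p-value, so that a non-significant result is not read as no effect.

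The cost is one paragraph, one added interval estimate and a less favourable stated power. No extra patients are proposed, and the primary test is unchanged.
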